4.10.2 Laboratory Test Results

Blood and urine samples will be collected by site staff for clinical laboratory testing. Urine pregnancy tests will be performed at the site and will be recorded in the eCRF as “Positive” or “Negative”. All other samples will be analyzed at the central laboratory. For all samples collected, the following data will be recorded in the eCRF: test category (ie, Chemistry, Hematology, Urinalysis, Coagulation, Pregnancy Test, Viral Serology or Urine Drug Screen), sample collection date, and sample time. For urine pregnancy tests, the result will also be recorded in the eCRF as “Positive” or “Negative”. An indicator for whether a repeat sample was taken (Yes/No) will also be recorded in the eCRF for each sample collected.

Collected laboratory samples will then be processed at the central laboratory for the calculation of reported values for the laboratory tests listed in [Appendix 3](#). Central laboratory data will include test category, lab test name, reported result, reported unit, reported reference range (ie, low and high), and abnormal indicator. Data from the central laboratory will be combined with the laboratory eCRF data prior to analysis.

Change from baseline values to each post-baseline assessment will be calculated for all continuous laboratory tests.

4.10.3 Vital Sign Results

The following vital sign data will be recorded in the eCRF: assessment date, height, weight, BMI, as well as standing and supine temperature, pulse rate, respiratory rate, supine systolic blood pressure (BP), and diastolic BP. An indicator for whether a repeat assessment was taken (Yes/No) will also be recorded in the eCRF for each assessment.

Change from baseline values to each post-baseline assessment will be calculated for pulse rate, respiratory rate, systolic BP, and diastolic BP. In addition, potentially clinically important flags will be derived for systolic BP, diastolic BP, pulse rate, and respiratory rate (see [Table 1](#)).

Table 1: Potentially Clinically Important Criteria for Vital Sign Results

ECG measure	Lower PCI criterion	Upper PCI criterion
Pulse rate	≤50 bpm	≥130 bpm
Systolic BP	<90 mmHg	>130 mmHg
Diastolic BP	<50 mmHg	>85 mmHg
Change in systolic BP	decrease ≥30 mmHg	increase ≥30 mmHg
Change in diastolic BP	decrease ≥30 mmHg	increase ≥30 mmHg

BP = blood pressure; PCI = potentially clinically important

4.10.4 Electrocardiogram Results

Standard 12-lead electrocardiograms (ECGs) will be performed after the participant has been supine for approximately 5 minutes. All ECGs will be performed using the equipment supplied by the central ECG vendor. For all ECGs performed, the following data will be recorded in the eCRF: assessment date, triplicate timepoint, timepoint performed indicator (Yes/No), and time of assessment.

Electronic ECG tracings will be analyzed for the calculation of reported values for the following ECG tests: heart rate, RR interval, PR interval, QRS duration, QT interval, corrected QT interval using the Bazett formula (QTcB), corrected QT interval using the Fridericia formula (QTcF), evaluator interpretation, and abnormal findings. ECG vendor data will include ECG test name, reported result/finding, reported unit, standard result/finding, standard unit, and lead location. The evaluator interpretation result will be recorded as “NORMAL”, “ABNORMAL”, or “UNABLE TO EVALUATE”. Data from the ECG vendor will be combined with the ECG eCRF data prior to analysis.

Change from baseline values to each post-baseline assessment will be calculated for heart rate, RR interval, PR interval, QRS duration, QT interval, and QTcF interval. In addition, potentially clinically important flags will be calculated for heart rate, PR interval, QRS duration, QT interval, QTcB interval, QTcF interval, change from baseline in heart rate, and change in QT, QTcB, and QTcF intervals (see [Table 2](#)).

Table 2: Potentially Clinically Important Criteria for ECG Results

ECG measure	Lower PCI criterion	Upper PCI criterion
Heart rate	≤50 bpm	≥130 bpm
PR interval		≥180 msec
QRS duration		≥100 msec
QT interval		≥450 msec
QTcB interval		≥450 msec
QTcF interval		≥450 msec
Change in QTcB		increase ≥30 msec
Change in QTcF		increase ≥30 msec

ECG = electrocardiogram; PCI = potentially clinically important

4.10.5 Physical Examination

Physical examinations will be performed per the SOA. The date of the physical exam will be recorded in the eCRF. Any significant findings from physical examinations should be reported as either medical history or adverse events.

4.10.6 Columbia–Suicide Severity Rating Scale

The Columbia–Suicide Severity Rating Scale (C-SSRS; available at www.cssrs.columbia.edu) is a semi-structured interview that captures the occurrence, severity, and frequency of suicide-related thoughts and behaviors during the assessment period. The interview includes definitions and suggested questions to solicit the type of information needed to determine if a suicide-related thought or behavior has occurred. The C-SSRS has a “Screening/Baseline” version that will be completed at the Screening Visit (Visit 1) and a “Since Last Visit” version that will be completed at all other visits. Both versions contain all 11 categories of suicidal ideation and behavior defined in the Food and Drug Administration (FDA) guidance document on suicidal behavior and ideation (FDA, 2012). Each category is assessed using a single question requiring a “Yes” or “No” response with follow-up questions for any “Yes” responses. The assessment date and each C-SSRS response will be recorded in the eCRF.

In addition, three C-SSRS composite indicator variables will be calculated as follows:

4.10.6.1 C-SSRS Suicidal Ideation Indicator

A composite indicator of C-SSRS suicidal ideation will be calculated as:

- If the response to any one of the five suicidal ideation questions is “Yes”, THEN set the suicidal ideation indicator equal to 1.
- OTHERWISE, set the suicidal ideation indicator equal to 0.

4.10.6.2 C-SSRS Suicidal Behavior Indicator

A composite indicator of C-SSRS behavior ideation will be calculated as:

- IF the response to any one of the five suicidal behavior questions is “Yes”, THEN set the suicidal behavior indicator equal to 1.
- OTHERWISE, set the suicidal behavior indicator equal to 0.

4.10.6.3 C-SSRS Suicidal Ideation or Behavior Indicator

A composite indicator of C-SSRS suicidal ideation or behavior will be calculated as:

- IF the response to any one of the 5 suicidal ideation questions or any of the 5 suicidal behavior questions is “Yes”, THEN set the suicidal ideation or behavior indicator equal to 1.
- OTHERWISE, set the suicidal ideation or behavior indicator equal to 0.

4.11 Pharmacokinetic Variables

Plasma samples will be collected by site staff for PK testing. For all PK samples collected, the following data will be recorded in the eCRF: scheduled timepoint, sample collection date, and sample collection time. A validated bioanalytical method will be utilized for the determination of plasma concentrations of PRAX-944 and its metabolites, as applicable. For Part A, PK parameters of parent drug and primary metabolites (M15, M23, and M32) will be estimated from concentration-time data using noncompartmental methods as described in a separate PK analysis plan.

5 ANALYSIS METHODS

Analysis will be carried out using SAS® (version 9.4 or newer, SAS Institute Inc, Cary, NC). Templates for the summary tables, figures, and participant data listings will be available separately. Data listings will include all data recorded for all enrolled participants; where captured, data entered for screen failure participants will be flagged in the listings.

For all data displays, separate summaries will be generated for each part and phase (open-label titration and double-blind randomized withdrawal) of the clinical trial.

- Part A: All summaries except those for adverse events will use a single "PRAX-944 Overall" column. Summaries of adverse events will use the following columns: "PRAX-944 20 mg qAM", "PRAX-944 40 mg qAM ", and "PRAX-944 Overall".
- Part B: Summaries of disposition and PK will be presented for all of Part B (i.e., not by phase) and will use a single "PRAX-944" column.
- Part B Open-label Titration: Summaries of demographics, baseline characteristics, medical history, prior and concomitant medications, study drug exposure, efficacy, and all safety except adverse events will include a "PRAX-944 Overall" column. Summaries of adverse events will include columns for "PRAX-944 20 mg qAM", "PRAX-944 40 mg qAM ", "PRAX-944 60 mg qAM ", "PRAX-944 80 mg qAM ", "PRAX-944 100 mg qAM ", "PRAX-944 120 mg qAM ", and "PRAX-944 Overall".
- Part B Randomized Withdrawal: Summaries of demographics, baseline characteristics, medical history, prior and concomitant medications, study drug exposure, efficacy, and all safety except adverse events will include the columns "Placebo" and "PRAX-944" for the randomized withdrawal phase. Summaries of adverse events will include columns for "Placebo" and "PRAX-944".

Descriptive statistics for continuous data will include number of participants (n), mean, standard deviation (SD), median, minimum, and maximum. Summaries of change from baseline variables will include only participants who have both a baseline value and corresponding value at the timepoint of interest. Descriptive statistics for categorical data will include frequency and percentage. Where appropriate, descriptive statistics may be presented with 95% confidence intervals (CIs).

The minimum and maximum will be reported with the same degree of precision (ie, the same number of decimal places) as the recorded data. Measures of location (eg, mean and median) will be reported to 1 degree of precision more than the recorded data, and measures of spread (eg, standard deviation) will be reported to 2 degrees of precision more than the recorded data.

Any changes to the analyses that are not included in this SAP will be documented in the CSR.

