For all data displays, separate summaries will be generated for each part of the clinical trial. For the randomized portion of Part B, data will be summarized by the randomized continuation treatment. Safety, tolerability, PK, and efficacy variables will be summarized using descriptive statistics. Descriptive summaries for categorical variables will include counts and percentage. Descriptive summaries for continuous variables will include number of participants (n), mean, standard deviation (SD), median, minimum, and maximum. Where appropriate, 95% confidence intervals (CIs) may be reported. Summaries will be presented by time point, where appropriate.

Unless specified otherwise, all data recorded will be listed by participant.

Reported values and change from baseline values in TETRAS Upper Limb score, TETRAS Performance subscale total and individual scores, 

The Enrolled Analysis set includes all participants who sign an informed consent form and are provided with an enrollment number. The Enrolled Analysis set will be used for all participant disposition analyses.

The Safety Analysis set includes all participants who received at least 1 dose of study drug. Participants will be classified according to actual intervention received. The Safety Analysis set will be used for all demographic, baseline characteristics, prior/concomitant medication, study drug exposure, and safety analyses.

The Full Analysis set includes all participants who took at least 1 dose of study drug and have a valid Baseline TETRAS assessment and at least 1 valid post-Baseline TETRAS assessment. The Full Analysis set will be used for the analysis of all efficacy data.

The PK Analysis Set includes all participants who received at least 1 dose of study drug and have at least 1 evaluable plasma concentration. The PK Analysis Set will be used for the analysis of plasma concentrations and PK parameters.

[figure not shown]

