- c. Placement of an intrauterine device or intrauterine system.

Note:

- A participant can agree to using 2 methods, 1 of which is primarily dependent on their partner. For example, a male participant can agree to a barrier with spermicide and for his female partner to use oral hormonal contraception. Similarly, a female participant can agree to using oral hormonal contraception and for her male partner to use a barrier with spermicide.
- Male participants must use 2 highly effective methods from Day -1 through 90 days + 5 half-lives (3 days) after the last dose of study drug (ie, 93 days).
- Female participants must use 2 highly effective methods from Day -1 through 30 days + 5 half-lives (3 days) after the last dose of study drug (ie, 33 days).

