3.6 Pharmacokinetic Analysis Set

The pharmacokinetic (PK) analysis set includes all participants that received at least 1 dose of study drug and have sufficient PK concentration data for analysis. The PK Analysis set will be used for the descriptive statistical analysis of plasma concentrations and PK parameters.

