5.9 Pharmacokinetic Analyses

5.9.1 Plasma Concentrations

For each study part, plasma concentrations will be summarized by visit and nominal sampling time using descriptive statistics. For concentration summaries, plasma concentrations below the level of quantification (BLQ) will be set to zero. Descriptive statistics for plasma concentrations will include n, number of participants with concentrations below the level of quantification (BLQ), mean, SD, coefficient of variation (CV%), geometric CV%, geometric mean, median, minimum, and maximum. All plasma concentration data will be listed by study part, participant, and visit.

Plasma concentrations will also be presented graphically.

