e TETRAS can be completed anytime at Screening and Day 70. On other days, the following timing should be followed: Day 1: pre-dose and 6 (±2) hours after a 20 mg QAM dose Day 7: 6 (±2) hours after a 40 mg QAM dose Day 21: 6 (±2) hours after an 80 mg (or highest tolerated dose) QAM dose Day 42: pre-dose and 6 (±2) hours after a 120 mg (or highest tolerated dose) QAM dose Day 56: 6 (±2) hours post-dose

f The TETRAS Performance assessment will be captured on video for central reading. The local rater must rate the same TETRAS Performance assessment as that which is captured on video for central reading. The Screening video will also be independently assessed for eligibility.

Study Phase	Screening		Open-label Titration									
Visit Days (Visit Window)	Day -28 to Day -1		Day 1 (Baseline)	Day 3	Day 7	Day 14	Day 21	Day 28	Day 35	Day 41		Day 42
		Day -2 (-2)										

g Kinesia ONE assessments must be completed immediately after the TETRAS Performance assessments (including both pre-dose and post-dose assessments on Day 1 and Day 42). After each TETRAS Performance assessment, Kinesia ONE assessments should be completed twice separated by at least 30 minutes. All 3 maneuvers in the upper limb item (sub-items 4a, 4b, and 4c) will be completed for both arms, first for the RIGHT arm and then for the LEFT.

h For visits with multiple TETRAS assessments, the TETRAS ADL subscale should only be assessed once. On Day 1, the ADL subscale should be completed pre-dose. On day 42, the ADL subscale should be completed 6 (±2) hours after the QAM dose.

i On Day 1 and Day 42 blood samples should be collected at the following timepoints: pre-dose and 0.5, 1, 2, 4, and 6 hours post-dose. The 6-hour post-dose sample will be collected immediately after completion of the second Kinesia ONE assessment. When PK sampling timepoints coincide with the TETRAS Performance timepoints or accelerometer-based assessment timepoints, the PK sample is to be obtained last. On Days 7, 21, and 56; samples should be collected 2 hours post-dose. Blood collection can be completed anytime on Day 70.

j Participants will be randomized (1:1) to receive either placebo or PRAX-944 from Day 43 to Day 56. Randomization can occur on Day 37 through Day 42.

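### Part B concentrations are tabulated in one PRAX-944 column, so the Day 56 row mixes active and placebo participants and would show about half the true exposure

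*SAP*

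**What the plan says.** SAP Section 5 opens with a general rule that displays are separated by study part and phase. It then makes an exception for Part B: "Summaries of disposition and PK will be presented for all of Part B (i.e., not by phase) and will use a single" column, headed PRAX-944. The Placebo and PRAX-944 columns defined for the randomized withdrawal phase cover demographics, exposure, efficacy, safety and similar displays, but PK is not in that list.

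SAP 5.9.1 tabulates concentrations for each part by visit and nominal sampling time, with no treatment split. It adds: "For concentration summaries, plasma concentrations below the level of quantification (BLQ) will be set to zero". Besides n and the BLQ count, the statistics requested are "mean, SD, coefficient of variation (CV%), geometric CV%, geometric mean, median, minimum, and maximum".

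The Part B schedule (SAP Appendix 1, footnotes i and j; the same footnotes are in Protocol Table 3) says: "On Days 7, 21, and 56; samples should be collected 2 hours post-dose". It also says: "Participants will be randomized (1:1) to receive either placebo or PRAX-944 from Day 43 to Day 56".

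The PK analysis set (SAP 3.6) "includes all participants that received at least 1 dose of study drug and have sufficient PK concentration data for analysis". It is defined per participant, so someone switched to placebo qualifies through open-label samples.

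The protocol rule, in the Synopsis and again in Section 9.3, is: "For the randomized portion of Part B, data will be summarized by the randomized continuation treatment". The next sentence in both places names PK among the variables to be summarized.

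**The concern.** Followed as written, the Day 56 row of a column headed PRAX-944 contains every Part B participant sampled that day, about half of whom took their last active dose on Day 42. Their zeros are averaged with the active arm's concentrations.

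Day 56 is the only scheduled sample on PRAX-944 after Day 42, so this row is the only tabulated exposure for the blinded active arm. Read at face value, it would say that exposure fell by about half in two weeks at an unchanged dose and became highly variable. A BLQ count near one half under an active-drug heading could also be taken for non-adherence, since Protocol 6.4 lists plasma exposure as one measure of compliance.

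The layout departs from the protocol's rule for the randomized portion. SAP 7.1 does not list it; the only PK change there concerns the Part A serial sampling.

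**Working it through.** The plan gives no figure for this point, so there is nothing of its own to reproduce. The check has two steps.

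**1. Are the placebo-arm Day 56 samples expected to be BLQ?**

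The only half-life information is in Protocol 5.4.3: "30 days + 5 half-lives (3 days) after the last dose of study drug".

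- Half-life: 3 × 24 h / 5 = 14.4 h.
- Time from the morning dose on Day 42 to two hours after the Day 56 dose: 14 × 24 + 2 = 338 h.
- Number of half-lives: 338 / 14.4 = 23.5. Fraction remaining: 0.5^23.5, about 9 × 10⁻⁸.

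The 14.4 h figure comes from a washout allowance, so longer half-lives were tried as assumptions. At 24 h, 0.006% remains (14.1 half-lives). At 48 h, 0.8% remains (7.0 half-lives). If that 0.8% were still quantifiable, the pooled mean with equal arms would be 0.5 × 1 + 0.5 × 0.008 = 0.504 of the active mean, so the result does not hinge on the assay limit.

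**2. What would the pooled row show?**

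Let f be the share of participants on active drug, m and c the active-arm mean and CV, and let all placebo values be zero.

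- Pooled mean = f·m.
- Pooled variance = f(1 + c²)m² − f²m².
- Pooled CV = √[(1 + c²)/f − 1]. At f = 1/2 this is √(1 + 2c²), which is at least 100% for any c.

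The documents give no value for c; 30% to 50% is assumed. For 12 participants:

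| Active:placebo | Pooled mean | CV, c = 0 | CV, c = 30% | CV, c = 50% |
|---|---|---|---|---|
| 5:7 | 0.42 m | 118% | 127% | 141% |
| 6:6 | 0.50 m | 100% | 109% | 122% |
| 7:5 | 0.58 m | 85% | 93% | 107% |

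With 24 participants split 12:12, the mean is again 0.50 m.

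These are population CVs; the table would use the sample SD. At 6:6, with c also taken as a sample CV, c² is multiplied by 5/6 and the result by √(12/11) = 1.044:

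- c = 30%: √(1 + 2 × 0.075) × 1.044 = 112%.
- c = 50%: √(1 + 2 × 0.208) × 1.044 = 124%.

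At 6:6 the median is the average of a zero and the lowest active value, that is, half the lowest active value. At 5:7 it is zero. Any zero makes the geometric mean zero and its logarithm undefined, so the geometric CV cannot be computed.

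An invented example: active values 60, 80, 90, 110, 120 and 140 have mean 100, sample CV 29%, median 100 and geometric mean 96. Adding six zeros gives mean 50, sample CV 112% (SD = √(34200/11) = 55.8), median 30 and geometric mean 0.

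**The case against.** The best counter-argument is that the layout is not certain. The table shells are kept separately and were not available. The column heading could be meant as active-treated participants only. The bullet that sets the single column already sits badly with SAP 5.1, which summarizes disposition, including the number randomized, by treatment group. None of this cures the text. The same column is assigned to disposition for all of Part B, placebo participants included; 5.9.1 has no treatment split; and a shell that did split by arm would contradict Section 5.

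Second, the harm is small. No visible primary or secondary endpoint uses PK, and no test or safety conclusion changes. The BLQ count is tabulated and every concentration is listed. Day 42 supplies six timepoints before the switch. By-visit rows already mix dose levels, because some participants will be on a lower dose than planned. All of this stands and limits the weight of the point, but the row would still be mislabelled.

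Third, BLQ is an inference. The half-life is back-calculated, no assay limit is stated, and SAP 4.11 allows for metabolites whose half-lives are not given. The inference is robust for parent drug, but it does not extend to metabolites.

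Fourth, the conflict between zeros and geometric statistics is a separate gap that would exist without pooling, for example at Day 1 pre-dose. That is correct; it is raised here because pooling brings it into an on-treatment row.

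**Conclusion.** The concern holds. As written, the SAP produces a Day 56 row that does not describe PRAX-944 exposure, and it departs without acknowledgement from the protocol's rule for the randomized portion.

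With equal arms the mean is understated by half, and the CV is at least 100% whatever the true variability. Two of the statistics the SAP asks for, the geometric mean and geometric CV, are zero or cannot be computed. The result rests on the planned 1:1 split surviving roughly to Day 56 and on parent drug being near zero after 14 days. The specific CV figures also rest on the assumed active-arm CV.

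The damage is limited to a descriptive table. Efficacy is not affected: SAP 3.5, 5 and 5.7 already provide by-arm displays for the withdrawal phase. Day 70 pools the same arms but matters little, because on the same half-life both should be BLQ by then (14 days off drug for the active arm, 28 for placebo).

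**What to change.** In SAP 5 and 5.9.1, present Day 56 concentrations in separate Placebo and PRAX-944 columns by blinded-phase treatment. Say whether that means treatment as randomized, which is the protocol's wording, or as actually received. The single column can stay through Day 42; Day 70 can follow the Day 56 columns.

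Add one sentence on geometric statistics when BLQ values are present. Either do not report them if any value is BLQ, or compute them on quantifiable values with the BLQ count alongside. The same rule is needed for Day 1 pre-dose and would serve Day 70.

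If the single column is kept on purpose, list it with its reason in SAP 7.1 as a change from the protocol.

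The cost is SAP wording and one table shell, with no new data. The price is smaller columns at Day 56: about 6 participants each if 12 are enrolled, or 12 each if 24. The active column would still combine different final dose levels.

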7. DISCONTINUATION OF STUDY DRUG AND PARTICIPANT DISCONTINUATION/WITHDRAWAL

7.1. Discontinuation of Study Drug

In rare instances, it may be necessary for a participant to permanently discontinue study drug. If study drug is permanently discontinued, the participant will remain in the clinical trial to be evaluated for safety and efficacy. See the SoA for data to be collected at the time of early termination for each part, if applicable.

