3.5 Randomized Withdrawal Analysis Set

The randomized withdrawal analysis set is a subset of the full analysis set and includes all participants who were randomized into the double-blind, randomized withdrawal phase of Part B and have a valid Day 42 TETRAS assessment and at least 1 valid TETRAS assessment after Day 42. The randomized withdrawal analysis set will be used for the analysis of all efficacy data collected during the randomized withdrawal phase.

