5.1 Participant Disposition

All participants in the enrolled analysis set will be included in disposition summaries. The number of participants screened, screen failed, randomized, completed, and discontinued from the study, as well as reason for discontinuation, will be summarized by treatment group and overall. The number of participants in each analysis set will also be summarized. All disposition data will be listed by participant.

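### The SAP's single PRAX-944 column for Part B disposition contradicts SAP 5.1 and the protocol, and would hide dropout by randomized arm in that table

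*SAP*

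**What the plan says.** Four statements govern how Part B disposition is displayed.

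- SAP section 5, Part B bullet: "Summaries of disposition and PK will be presented for all of Part B (i.e., not by phase) and will use a single" column, which is headed PRAX-944.
- SAP section 5, sentence introducing the bullets: "For all data displays, separate summaries will be generated for each part and phase (open-label titration and double-blind randomized withdrawal").
- SAP 5.1, the section on disposition itself, covers the numbers screened, screen failed, randomized, completed and discontinued, and adds: "as well as reason for discontinuation, will be summarized by treatment group and overall".
- Protocol 1.1 (Statistical Methods), repeated in protocol 9.3: "For the randomized portion of Part B, data will be summarized by the randomized continuation treatment".

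The randomized-withdrawal bullet of SAP section 5 gives Placebo and PRAX-944 columns to demographics, exposure, efficacy, safety and adverse events, but does not mention disposition. SAP 7.1, which records departures from the protocol, does not mention the single column.

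**The concern.** In a randomized withdrawal phase, who leaves after the switch, from which arm and why is informative about both efficacy and tolerability. A placebo participant may leave because tremor returned. A participant kept on PRAX-944 may leave because of an adverse event. A single column places both in the same row, together with anyone who left during open-label titration, and labels all of them PRAX-944.

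The split also matters for reading the efficacy results of that phase. The randomized withdrawal analysis set (SAP 3.5) requires participants to "have a valid Day 42 TETRAS assessment and at least 1 valid TETRAS assessment after Day 42". Someone who leaves soon after the switch with no further TETRAS drops out of the set, and the early termination visit that could supply one is to be done only if possible (protocol 7.2). A disposition table by arm is where a reader would first look to see whether such losses were balanced.

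**Working it through.** The documents give no figure on this point, so there is nothing to reproduce. The check has three parts.

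**1. Can the four statements be reconciled?** The single-column bullet can be read as a deliberate exception to the general sentence that introduces it, since the specific instruction normally governs. That does not settle the conflict with SAP 5.1, which is equally specific to disposition, asks for treatment groups and includes a count of participants randomized. Nor does it settle the conflict with the protocol, because SAP 7.1 declares no change. A programmer cannot follow both the bullet and SAP 5.1.

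**2. What would the pooled column conceal?** Inputs: about 12 participants in Part B, up to 24 (protocol 5.1.2 and 9.1); 1:1 randomization (protocol 4.1.2.2.2). Assumptions: everyone is randomized, the split is exactly equal, nobody leaves during titration, and the dropout counts are invented for illustration.

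Rate by arm = dropouts in arm / (N/2). Pooled rate = all dropouts / N.

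| N | Placebo | PRAX-944 | Pooled column |
|---|---|---|---|
| 12 | 2/6 = 33% | 0/6 = 0% | 2/12 = 17% |
| 12 | 1/6 = 17% | 1/6 = 17% | 2/12 = 17% |
| 12 | 0/6 = 0% | 2/6 = 33% | 2/12 = 17% |
| 24 | 4/12 = 33% | 0/12 = 0% | 4/24 = 17% |
| 24 | 0/12 = 0% | 4/12 = 33% | 4/24 = 17% |

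The pooled entry is the same whether all the dropout is on placebo, all on PRAX-944 or, as in the second row, evenly shared.

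**3. Do other planned outputs supply the split?**

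- *Adverse events.* TEAEs leading to study drug withdrawal are summarized by part and phase, with both arms shown after randomization (SAP 5, 5.8.1, 5.8.1.2). They cover only AE-related stopping of drug. Protocol Appendix 2 says lack of efficacy in itself is not reported as an AE, although resulting symptoms are if they meet the AE definition. SAP 5.8.1 also bases these tables on the randomized withdrawal analysis set, whereas SAP 5.8 names the randomized withdrawal safety set. Under SAP 5.8.1, a dropout with no TETRAS after Day 42 would be missing here too.
- *Counts by arm.* Comparing the number in the randomized withdrawal safety set (SAP 3.3 and 5.3) with the number in the efficacy summaries shows how many dosed participants are missing from efficacy, by arm. It gives no reasons and misses anyone randomized but never dosed.
- *Listings.* SAP 5.1 adds: "All disposition data will be listed by participant". SAP section 3 carries randomized and actual treatment in every analysis data set. Dropout by arm can therefore be rebuilt by hand.
- *Stopping drug.* Protocol 7.1 says: "If study drug is permanently discontinued, the participant will remain in the clinical trial to be evaluated for safety and efficacy". SAP 4.1 and 5.1 deal with completing or leaving the study, so stopping drug while staying in the study has no row in the disposition table. SAP section 3 names a reason-for-treatment-discontinuation variable, but SAP 4.1 describes collection only of reasons for early withdrawal from the study.

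**The case against.** The strongest reply is that the layout is not settled and little is lost. SAP 5.1 and the protocol both point to a display by arm, and the table templates are held separately and cannot be seen here. With about 12 to 24 participants plus replacements, the listings are short enough to read directly. Everyone in Part B is planned to take PRAX-944 through Day 42, so the heading describes study-level exposure. Part B's primary objective is safety, randomized-phase adverse events already have both arms, and the visible primary and secondary endpoints end at Day 42.

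Much of this stands. A reader might infer that differential dropout could not be seen anywhere in the report, or that the disposition table is the only check on bias in the efficacy set. The documents do not support either: listings, treatment variables, by-arm counts and the AE table each recover part of the picture. A reader might also infer that placebo dropouts would count against PRAX-944 in a result. They would not, because the label enters no estimate or test.

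The reply does not remove the contradiction. It also leaves the table mislabeled after Day 42 if the bullet is followed, and it offers no planned summary that gives withdrawals with reasons by arm.

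**Conclusion.** The point holds as an internal contradiction with a practical consequence. If the single-column rule is followed, withdrawals on placebo after Day 42 are tabulated under PRAX-944, and the disposition table cannot show differential dropout. The split would have to be rebuilt from listings, because the by-arm AE tables cover only AE-related stopping and the by-arm counts carry no reasons.

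In the illustration, a contrast of 33% versus 0% appears as 17%. Those dropout counts are assumed. The true denominators will also differ, because disposition uses the enrolled set (SAP 3.1 and 5.1), some participants may leave during titration, and up to 6 in Part B may be replaced (protocol 5.1.3). The figures show what pooling hides and do not forecast the table.

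This is a reporting defect that should be corrected. It does not threaten a primary analysis, and the text gives no ground for reading it as an intention to conceal the placebo arm.

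**What to change.** Remove disposition from the single-column rule in SAP section 5, so that it agrees with SAP 5.1 and the protocol. Present Part B disposition by phase:

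- open-label titration under PRAX-944;
- randomized withdrawal under Placebo, PRAX-944 and overall.

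In each phase, show study withdrawal with its reason. Where the reason-for-treatment-discontinuation variable named in SAP section 3 is in fact collected, add permanent study drug discontinuation with reason as a separate row.

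The cost is SAP wording and one table shell. The split by phase and arm uses data already planned. The drug-discontinuation row depends on confirming that reasons other than adverse events are captured, because the variable list in SAP section 3 is the only evidence that they are.
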